3. PARTICIPANT SELECTION AND ENROLLMENT PROCEDURES

3.1 Inclusion Criteria

- ≥ 18 years-old
- Biopsy-proven prostate adenocarcinoma
- Planned prostatectomy with lymph node dissection
- Intermediate to high-risk disease (as determined by elevated PSA [$PSA > 10$], T-stage [$T2b$ or greater], Gleason score [Gleason score > 6] or other risk factors)
- Able to provide written consent.
- Karnofsky performance status of ≥ 50 (or ECOG/WHO equivalent)
- Diagnostic CT or MRI performed within 90 days of the research PET

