10.2 Determination of Sample Size and Accrual Rate

10.2.1 Sample Size and Power Estimate

The estimated sample size will be 200 patients to adequately power the primary aim. The power analysis will be based on the comparison of sensitivity between conventional imaging and PSMA-11 PET. With a power of 80% and a significance level of 0.01, a sample size of 61 patients with nodal metastases is required. The following assumptions are made:

- i. 30% of intermediate to high-risk patients have nodal metastases at prostatectomy.

- ii. 25% of patients will not undergo the planned prostatectomy. Patients that do not undergo prostatectomy will not be included in the analysis population, and will not undergo central imaging review.
- iii. Conventional imaging has a 45% detection sensitivity for nodal metastases on a per-patient basis (2).
- iv. PSMA-11 PET has a 65% detection sensitivity for nodal metastases on a per-patient basis.

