10.3.4 Analysis of Exploratory Endpoints

PPVs on a per-patient and per-region-basis of ^{68}Ga -PSMA-11 PET for detection of tumor location confirmed by histopathology/biopsy and conventional imaging follow-up will be calculated and reported along with the corresponding two-sided 95% confidence intervals. The paired McNemar's test will be used to compare the PPVs of ^{68}Ga -PSMA-11 PET imaging to the PPVs of conventional imaging.

Sensitivity, specificity, and NPVs on a per-patient basis of ^{68}Ga -PSMA-11 PET for detection of tumor location confirmed by histopathology/biopsy will be summarized in tabular format. Furthermore, the positive and negative likelihood ratios (LR+ and LR-) will be calculated and reported. 95 confidence intervals of sensitivity, specificity, and NPV will be calculated using the Wilson score method. The comparisons of sensitivity, specificity, and NPV on a per-patient basis of ^{68}Ga -PSMA-11 PET imaging will be compared to of sensitivity, specificity, and NPV on a per-patient basis of conventional imaging using a paired McNemar's test.

Detection rates on a per-patient basis of ^{68}Ga -PSMA-11 PET stratified by PSA value (0.2 to < 0.5; 0.5 to < 1.0; 1.0 to < 2.0; 2.0 to < 5.0; ≥ 5.0) will be summarized in tabular format and compared between PSA strata using chi-square analysis. The impact of ^{68}Ga -PSMA-11 PET on clinical management in BCR patients will be evaluated using descriptive statistics.

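### Section 10.2.1 gives 61 node-positive patients 80% power for PET versus conventional imaging without naming a test, sidedness or discordance; under the paired McNemar test of 10.3.4, 61 suffices only if very few metastases seen on conventional imaging are missed by PET

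*Combined protocol and SAP*

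**What the plan says.** Section 10.2.1 sizes the trial to power the primary aim and explains how: "The power analysis will be based on the comparison of sensitivity between conventional imaging and PSMA-11 PET". It then gives the result: "With a power of 80% and a significance level of 0.01, a sample size of 61 patients with nodal metastases is required". The assumed per-patient sensitivities are 45% for conventional imaging, taken from a cited source, and 65% for PSMA-11 PET. The section does not name a test or formula, say whether the 0.01 is one- or two-sided, or say how often the two modalities are expected to disagree.

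Both modalities are available in the same men, because section 3.1 requires "Diagnostic CT or MRI performed within 90 days of the research PET". Section 10.3.4, under exploratory endpoints, says that PET sensitivity, specificity and NPV will be compared with those "on a per-patient basis of conventional imaging using a paired McNemar's test". No other test of this comparison appears in the plan. The primary success rule in 10.3.2 uses fixed thresholds (sensitivity 65%, specificity 90%, in 2 of 3 readers) and no comparator.

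**The concern.** The power of McNemar's test depends on the discordant pairs: node-positive men found by PET only, against those found by conventional imaging only. Two marginal sensitivities do not determine a sample size for it; a discordance rate is also needed, and 10.2.1 gives none. What does yield 61 from the stated inputs alone is a one-sample test against a constant 45%. That calculation carries no sampling error for conventional imaging, although the trial would estimate its sensitivity in the same men.

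At stake is how the comparison will be read. If the McNemar result is not significant, a reader of 10.2.1 would take it to come from a test with 80% power when the power may be well below that. This holds even if 61 node-positive men are obtained. How many such men 200 enrolments will yield, and how likely the success rule is to be met, are separate questions.

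**Working it through.** **Inputs.** From 10.2.1: p0 = 0.45, p1 = 0.65, difference d = 0.20, alpha = 0.01, power 80% (z = 0.842). Sidedness is not stated, so both are shown (z = 2.326 one-sided, 2.576 two-sided). Let c be the share of node-positive men found by conventional imaging and missed by PET. The documents do not give c, so it is an assumption, varied from 0 to 15.75%. The upper end is independence of the two modalities: 0.45 × 0.35 = 0.1575.

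**Step 1: reproduce 61.** One-sample score test against a fixed 45%:

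n = [z_alpha √(p0(1−p0)) + z_beta √(p1(1−p1))]² / d²

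- One-sided: (2.326 × √0.2475 + 0.842 × √0.2275)² / 0.04 = 60.74, so **61**.
- Two-sided: 70.8, so 71.

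Other one-sided one-sample forms give 58 (alternative variance), 62 (arcsine), 63 (null variance) and 66 (continuity-corrected). An exact binomial test has 72% power at 61 and first reaches 80% at 66. Two independent groups would need 123 per group one-sided or 144 two-sided.

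**Step 2: the paired test.** The PET-only share is c + 0.20, so total discordance is ψ = 0.20 + 2c. In the normal approximation for McNemar's test:

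n = [z_alpha √ψ + z_beta √(ψ − d²)]² / d²

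Power at n = Φ{[d√n − z_alpha √ψ] / √(ψ − d²)}

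Example, c = 5%, two-sided: ψ = 0.30, so n = (2.576 × √0.30 + 0.842 × √0.26)² / 0.04 = 84.6, i.e. 85. Power at 61 = Φ[(0.2 × √61 − 2.576 × √0.30) / √0.26] = Φ(0.30) = 62%.

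| c | ψ | n for 80%, one-/two-sided | Power with 61, one-/two-sided |
|---|---|---|---|
| 0 | 0.20 | 48 / 56 | 90% / 85% |
| 1% | 0.22 | 53 / 62 | 87% / 80% |
| 5% | 0.30 | 73 / 85 | 71% / 62% |
| 10% | 0.40 | 98 / 114 | 56% / 46% |
| 15.75% (independence) | 0.515 | 127 / 148 | 44% / 34% |

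**Step 3: the c at which 61 suffices.** Setting n = 61 gives c = 2.7% one-sided (ψ = 0.254) or 1.0% two-sided (ψ = 0.219). That is 0.027 × 61 = 1.6 men, or 0.0096 × 61 = 0.6 of a man.

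**Step 4: sensitivity to method.** The exact conditional test puts the limit at about 2.3% one-sided and 1.3% two-sided. Miettinen's formula, the most lenient tried, puts it at just under 4% one-sided and 2.3% two-sided. Enumerating all outcomes at n = 61, two-sided, power is 83% (exact test) to 89% (asymptotic test) at c = 1%, and 56% to 64% at c = 5%. The choice of method shifts the limit by a percentage point or so and does not rescue c of 5% or more.

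**The case against.** Section 10.2.1 never uses the word paired, McNemar appears only among exploratory analyses, and the primary rule is single-arm. A benchmark test against a literature value of 45% would suit that design, and nowhere does the plan attach 80% power to the test in 10.3.4 by name. This stands as to scope: the point is about what 61 is claimed to power, and it leaves the primary success rule untouched. It does not remove the problem, because 10.2.1 itself describes the power analysis as a comparison of the two modalities.

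A reader might infer that the sponsor used the one-sample formula, or that 61 is an arithmetic error. The documents support neither. The match shows which formula yields 61, not which was used, and a paired calculation with almost nested tests also gives 61. What can be said is that the decisive assumption is unstated.

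A reader might also infer that the comparison is underpowered under most plausible discordance. Nothing in the documents says which values are plausible. Independence is a harsh case, since both modalities should find larger nodes more easily, and section 2.1 describes the staging problem as small nodes that escape CT and MRI size criteria. Both considerations point towards a low c, though neither fixes it.

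Lastly, the 95% intervals in 10.3.4 do not contradict a planning alpha of 0.01. The gap there is only that the level of the McNemar test is not given.

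**Conclusion.** The concern holds as an undocumented, and possibly optimistic, power statement. The figure 61 reproduces exactly as a one-sided one-sample test against a constant 45%. Under the only test named for the comparison, 80% power with 61 requires that about 1% (two-sided) to 3% (one-sided), or at most about 4% by the most lenient method, of node-positive men be found by conventional imaging and missed by PET. At 5%, power is about 71% one-sided or 62% two-sided; under independence it is 44% or 34%. These figures rest on the plan's own 45%, 65% and 0.01, on the normal approximation, and on an assumed range for the conventional-only share.

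**What to change.** In 10.2.1, choose one of two statements.

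(a) Name the paired McNemar test, its sidedness, its alpha and the assumed share of node-positive men found by conventional imaging and missed by PET. Replace the single claim of 80% power at 61 with the power over a stated range of that share, for example the table above.

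(b) State that 61 is for a one-sided, one-sample test of PET sensitivity against a fixed 45%. Stop describing it as powering the comparison with conventional imaging, and say in 10.3.4 that the McNemar comparison is not powered at 80%.

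In either case, state in 10.3.4 the level at which the McNemar test will be judged. The cost is wording in two sections and a less favourable power statement. No extra patients, procedures or 99% intervals are needed.

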10.2.2 Accrual estimates

We anticipate enrolling 200 patients in total.

10.3 Analyses Plans

10.3.1 Analysis Population

All patients that undergo prostatectomy and have histology correlates will be included in the analysis for the primary endpoint.

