1. OBJECTIVE

Specific Aim

To evaluate ^{68}Ga -PSMA-11 PET/MRI for detection of regional nodal and distant metastases in patients with intermediate and high-risk prostate cancer scheduled to undergo prostatectomy with lymph node dissection.

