5.3 Image interpretation

1. ^{68}Ga -PSMA-11 PET

PET images will initially be interpreted in random order at separate reading sessions by 3 board-certified nuclear medicine physicians. Cross-sectional MRI imaging from the PET will be available for anatomic correlate. Final reads for each patient will be interpreted as positive or negative for the presence of pelvic nodal disease, and positive or negative for the presence of osseous metastatic disease and soft tissue metastases outside of the pelvis.

Clinical Follow-up

- a. Prostatectomy: patients without evidence of PSMA-11 PET positive nodal or metastatic disease noted on imaging will undergo radical prostatectomy. If a PSMA-11 PET positive regional pelvic node is noted, the urologist will be informed of the location of the suspicious node and the patient will undergo prostatectomy with nodal dissection.
 - i. Patients with nodes seen on PSMA-11 PET without positive nodes on pathology, will be rescanned with CT or MRI to determine if the suspicious node was thought to be removed. A PSMA-11 PET may be repeated as well at the discretion of the treating physician.
- b. If sites of PSMA-11 PET positive osseous or distant metastatic lesions are noted, the urologist will be informed, and further evaluation including further imaging (bone scan; NaF PET; CT; or MRI cross-section imaging) or targeted biopsy will be performed in order to restage the patient prior to the decision regarding whether or not a prostatectomy will be performed as per the responsible surgeon and standard of clinical care.

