- (2) Patients with extrapelvic nodal metastases will not be included in this analysis if patients do not undergo prostatectomy.

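### Unoperated patients get no central read, which can strip the extra-pelvic secondary analysis of key cases and leaves possible verification bias in the primary estimates unexamined

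*Combined protocol and SAP*

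**What the plan says.** The objective (section 1) concerns detection of metastases "in patients with intermediate and high-risk prostate cancer scheduled to undergo prostatectomy with lymph node dissection". The target population is therefore patients scheduled for surgery.

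The primary analysis population (section 10.3.1) is narrower: "All patients that undergo prostatectomy and have histology correlates will be included in the analysis for the primary endpoint".

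Assumption ii of section 10.2.1 is that "25% of patients will not undergo the planned prostatectomy". It continues: "Patients that do not undergo prostatectomy will not be included in the analysis population, and will not undergo central imaging review". The non-evaluable category in section 10.3.2 repeats the exclusion for one group: "Patients with extrapelvic nodal metastases will not be included in this analysis if patients do not undergo prostatectomy".

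Section 5.3, Clinical Follow-up, links the scan to surgery in two ways. Under item a, a patient with a PET-positive regional node goes on to prostatectomy with nodal dissection. Under item b, PET-positive bone or distant lesions are reported to the urologist and worked up further "in order to restage the patient prior to the decision regarding whether or not a prostatectomy will be performed".

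Sections 5.3 and 10.3.2 both describe three readers and a final read for each patient, covering pelvic nodes, bone and soft tissue outside the pelvis. Section 10.3.3 verifies the extra-pelvic findings by biopsy and follow-up imaging and names no analysis population. Section 10 plans no verification-bias correction, no bounds and no report of PET results in excluded patients.

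**The concern.** The scan under evaluation helps to decide who receives the reference standard, and those who do not receive it are neither analysed nor centrally read. There are two consequences.

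First, the extra-pelvic secondary analysis does not need surgery for verification. If assumption ii is applied as written, it still lacks three-reader results for patients whose surgery was cancelled because of distant PET findings. They are the patients most likely to supply its positive cases.

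Second, the success rule in section 10.3.2 compares point estimates with 65% sensitivity and 90% specificity, and the plan assumes a sensitivity of exactly 65%. A shift of a few points can decide either criterion. Without reader results for the unoperated patients, no correction on the trial's own reading method is possible.

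**Working it through.** **The plan's own figures.** Section 10.2.1 says "With a power of 80% and a significance level of 0.01, a sample size of 61 patients with nodal metastases is required". A one-sample normal approximation against a fixed 45% with one-sided alpha 0.01 reproduces this:

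- n = ((2.326 × √(0.45 × 0.55) + 0.842 × √(0.65 × 0.35)) / 0.20)² = 60.7, rounded up to 61.

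The plan's 200 patients, 25% without surgery and 30% nodal prevalence give 200 × 0.75 = 150 operated patients, of whom 150 × 0.30 = 45 are node-positive and 105 node-negative. The gap between 45 and 61 is a separate sample-size matter. The 150 are the base for what follows.

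**Operated patients at exactly 65% and 90%.**

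- True positives 45 × 0.65 = 29.25; false negatives 15.75.
- True negatives 105 × 0.90 = 94.5; false positives 10.5.
- PET-positive 39.75 of 150 = 26.5%.
- PPV = 29.25 / 39.75 = 0.736; NPV = 94.5 / 110.25 = 0.857.

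**Adding back the 50 unoperated patients.** Assume that PPV and NPV, given the regional PET result, are the same as in operated patients (the Begg-Greenes assumption). Let k of the 50 be node-positive on PET. Then

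- sensitivity = (29.25 + 0.736k) / (45 + 0.736k + 0.143(50 − k))
- specificity = (94.5 + 0.857(50 − k)) / (105 + 0.264k + 0.857(50 − k))

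| Assumption about the 50 | k | Sensitivity | Specificity |
|---|---|---|---|
| Same PET-positive rate as operated (26.5%) | 13.25 | 65.0% | 90.0% |
| 10 diverted by PET, 80% of them node-positive on PET; other 40 at 26.5% | 8 + 10.6 = 18.6 | 42.94 / 63.17 = 68.0% | 121.41 / 136.83 = 88.7% |
| Half node-positive on PET | 25 | 47.65 / 66.97 = 71.1% | 115.93 / 133.03 = 87.1% |

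**A second model.** The first model conditions on the regional result alone, whereas the trigger in section 5.3 is the distant result. So let regional accuracy itself differ in diverted patients. Add 10 to 30 diverted patients to the 150, with 50% to 90% truly node-positive, and regional PET positive in 80% to 90% of the node-positive and 30% to 50% of the node-negative. Values for the enlarged cohort are then 66.5% to 74.4% for sensitivity and 85.0% to 89.8% for specificity. If regional accuracy in diverted patients is also 65% and 90%, nothing changes.

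**Effect on the success rule.** Suppose instead that the cohort including diverted patients sits exactly at 65% and 90%. Take 20 diverted, 14 of them node-positive, with regional PET positive in 80% of the node-positive and 30% of the node-negative. The operated patients then show

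- sensitivity (0.65 × 59 − 0.80 × 14) / 45 = 60.3%
- specificity (0.90 × 111 − 0.70 × 6) / 105 = 91.1%

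For one reader, the binomial chance of at least 30 of 45 falls from 0.48 to 0.24, and the chance of at least 95 of 105 rises from 0.52 to 0.67.

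**The reading rule.** Sections 5.3 and 10.3.2 give every patient a final read. Section 10.2.1 withholds central review from the unoperated. Section 10.3.3 needs extra-pelvic reads but not surgery. If the final reads are the central review, these statements cannot all be followed.

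**The case against.** The strongest objection is that the trigger is distant disease. Section 5.3 sends patients with PET-positive regional nodes to surgery, so the analysis does not select on the regional result directly. That stands: bias in the primary estimates requires regional results or accuracy to differ in diverted patients. This is plausible, but the documents do not state it. It also means that a correction conditioned on the nodal result alone does not fit the protocol's mechanism.

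The 25% covers every reason for no surgery, and section 2.1 calls bone metastases rare at initial staging, although the same passage also names retroperitoneal nodes. Few patients may be diverted. With 10 diverted, the shifts in the table are 3.0 and 1.3 points, against binomial standard errors of √(0.65 × 0.35 / 45) = 7.1 and √(0.90 × 0.10 / 105) = 2.9 points. This stands as a limit on size. Unlike sampling error, however, the bias does not shrink with more patients.

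The primary objective is defined against pathology at prostatectomy, so an analysis of operated patients is legitimate. This stands too, and that analysis should be kept.

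Three stronger readings are tempting and are not supported:

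- **The secondary analysis loses its cases altogether.** Sections 10.3.1 and 10.3.2 restrict only the primary analysis, and patients with distant PET findings who still have surgery remain. The loss comes from one sentence among the sample-size assumptions.
- **The scans are read after surgery with pathology known.** Selecting scans by surgery status suggests later reading, but section 5.3 describes the reader interpretation ahead of clinical follow-up. The timing is unclear, and masking to pathology is simply not stated.
- **The bias can never be examined.** Section 5.3 requires PET findings to reach the urologist, so some clinical interpretation must exist for diverted patients. What would be missing is the three-reader result on which the success rule rests.

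**Conclusion.** The point holds in a limited form. As written, assumption ii of section 10.2.1 removes three-reader results for the patients most likely to have extra-pelvic disease from a secondary analysis that does not depend on surgery, and it conflicts with sections 5.3 and 10.3.2. That part follows from the text.

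The primary estimates may carry partial verification bias relative to patients scheduled for surgery. Its size is an assumption, because the number diverted by PET is not given: from no change, through about 3 points of sensitivity and 1 of specificity, to about 6 and 3 points if half of the unoperated are node-positive on PET. The direction rests on diverted patients being node-positive on PET more often than operated patients. In that case reported sensitivity is conservative and reported specificity is flattered, so the 90% criterion is the one at risk of false success. Correcting this is a cheap improvement; nothing here invalidates the primary analysis.

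**What to change.** Keep the histology-based primary analysis, and make these changes:

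1. Delete the clause in assumption ii of section 10.2.1 that withholds central imaging review. Have the same three readers read every scanned patient, masked to pathology and surgery status. Reconcile sections 5.3, 10.2.1, 10.3.2 and 10.3.3 accordingly.
2. In section 10.3.3, define the secondary population as all scanned patients with a biopsy or clinically obtained follow-up imaging. The study calendar (section 7) schedules no follow-up imaging, so this relies on what clinical care provides.
3. Tabulate regional and distant PET results by surgery status and by reason for no surgery.
4. Pre-specify a sensitivity analysis of the primary estimates: best-case and worst-case bounds, plus a verification-bias correction conditioned on both the regional and the distant PET result.

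The cost is about 50 scans × 3 existing readers = 150 additional reads and one sensitivity analysis. Patient care does not change.

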10.3.2 Analysis of Primary Endpoint

a) Imaging interpretation ^{68}Ga -PSMA-11 PET:

PET images will be interpreted by 3 different readers in a random order at separate reading sessions. Cross-sectional imaging from the PET will be available for anatomic correlate. Final reads for each patient will be interpreted as positive or negative for the presence of pelvic nodal disease, and positive or negative for the presence of osseous metastatic disease and soft tissue metastases outside of the pelvis.

Visual interpretation of PET data:

Regions of suspected disease will be graded on a two-point scale by each reader (0 = Negative or 1 = Positive). A region will be judged as positive if at least 1 lesion in this region is visually positive.

- i) Lymph nodes will be considered positive if the ^{68}Ga -PSMA-11 uptake is focal and greater than adjacent background. Pelvic lymph nodes will be subclassified according to their localization as follows: R/L obturator; R/L external iliac; R/L internal iliac; and other (total of 7 subgroups).
- ii) Visceral lesions will be considered positive if the ^{68}Ga -PSMA-11 uptake is focal and greater than physiologic background activity of the involvement organ or anatomic site.
- iii) Bone lesions will be considered positive if the ^{68}Ga -PSMA-11 uptake is focal and greater than physiologic bone marrow.
- b) Pathology analysis: Specimens from prostatectomy will be evaluated for the presence of nodal metastasis. This will be reported on a per-patient basis as positive or negative.
 - i) Nodes will be marked by location per site-specific protocol. For example if the urologist removed left and right nodal regions separately, then that patient will have two nodal regions (left/right). If a different surgeon removes nodes in six groups

(bilateral internal/external/obturator nodes), then that patient will have six nodal regions that will be analyzed.

- ii) Although not routinely performed during standard practice, immunohistochemical staining for PSMA-11 of tumor specimens (primary and lymph node metastases) may be performed, but is not required for this study.
- iii) The number of nodes counted on pathology will also be recorded.

c) Analysis plan for Primary Aim 1: For this study to reach success, 2 out of the 3 readers will have to demonstrate a detection sensitivity of 65% or greater for nodal metastases. Additionally, 2 out of the 3 readers will have to demonstrate a detection specificity of 90% or greater for regional nodal metastases based upon region as defined below on a per patient level. The sensitivity, specificity, positive and negative predictive value of PSMA-11 PET for the detection on a per patient basis will be determined using the below criteria:

- i) True positive patient:
 - (1) PSMA-11 PET-positive for regional nodes; pathology at prostatectomy positive for regional nodes. Region will be defined by the granularity used by the urologist at time of prostatectomy. Sensitivity will be calculated at a patient level by region, meaning that one correct region would make a true positive on a patient level. Only one node needs to correspond between imaging and pathology for a patient to be considered a true positive.
 - (2) PSMA-11 PET-positive for regional nodes; pathology negative for regional nodes; imaging after prostatectomy demonstrates node was not removed at surgery; and follow-up biopsy or imaging demonstrates presence of nodal disease.
 - (a) Criteria for positive node on follow-up imaging: imaging within 3 to 12 months; the node decreases by more than 30% (for patients undergoing systemic treatment or focal therapy at this site); or increase by more than 20% in short axis diameter in the absence of treatment (with a minimum of 3 mm in change in size).
- ii) True negative patient:
 - (1) PSMA-11 PET-negative for regional nodes; pathology at prostatectomy negative for regional nodes.
- iii) False positive patient:
 - (1) PSMA-11 PET-positive for regional nodes; pathology at prostatectomy is negative; and imaging after prostatectomy demonstrates that node is no longer present.
 - (2) PSMA-11 PET positive for regional node, but pathology at prostatectomy is positive for node but in a different nodal region than that node seen on PSMA-11 PET.

iv) False negative patient:

- (1) PSMA-11 PET negative for regional nodes, but pathology at prostatectomy is positive.

v) Non-evaluable:

- (1) PSMA-11 PET positive for regional nodes; pathology negative for regional nodes; imaging after prostatectomy demonstrates node was not removed at surgery; and no definitive follow-up is available.
- (2) Patients with extrapelvic nodal metastases will not be included in this analysis if patients do not undergo prostatectomy.

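### The 80% power in section 10.2.1 is offered for the primary aim but belongs to an exploratory comparison; the success rule in 10.3.2 c) has no stated power, and its 65% cut-off equals the assumed true sensitivity.

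*Combined protocol and SAP*

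**What the plan says.** Section 10.2.1 states: "The estimated sample size will be 200 patients to adequately power the primary aim". It names the basis of the calculation: "The power analysis will be based on the comparison of sensitivity between conventional imaging and PSMA-11 PET". The result follows: "With a power of 80% and a significance level of 0.01, a sample size of 61 patients with nodal metastases is required". The listed assumptions are 30% nodal prevalence, 25% of patients not reaching prostatectomy, 45% sensitivity for conventional imaging, and "PSMA-11 PET has a 65% detection sensitivity for nodal metastases on a per-patient basis". No test and no sidedness are named.

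Section 10.3.2 c), the analysis plan for Primary Aim 1, sets the success rule: "For this study to reach success, 2 out of the 3 readers will have to demonstrate a detection sensitivity of 65% or greater" and "Additionally, 2 out of the 3 readers will have to demonstrate a detection specificity of 90% or greater for regional nodal metastases". Conventional imaging does not appear in the rule.

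The same section reclassifies some patients. Under i)(2), a PET-positive, pathology-negative patient counts as a true positive if "imaging after prostatectomy demonstrates node was not removed at surgery; and follow-up biopsy or imaging demonstrates presence of nodal disease". Under iii)(2), a PET-positive patient counts as a false positive if "pathology at prostatectomy is positive for node but in a different nodal region than that node seen on PSMA-11 PET".

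The comparison with conventional imaging is listed as exploratory in the Synopsis and in section 2.5. Section 10.3.4 plans it as a paired McNemar test.

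**The concern.** Two parts of the plan describe different hypotheses under one label. The power statement concerns a difference between two imaging methods. The success rule concerns whether readers clear fixed cut-offs. A reader who puts them together will take 80% as the chance that the primary aim succeeds if PSMA-11 PET performs as assumed, but the plan supplies no such figure.

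The choice of cut-off adds to the problem. When the required observed value equals the assumed true value, the estimate falls on either side of it with roughly equal probability, whatever the sample size. What is at stake is how the result is read. A declared failure would look like failure in spite of 80% power, when a test performing exactly as assumed could miss the rule about half the time or more.

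**Working it through.** **Inputs.** From 10.2.1: 200 enrolled, 25% without prostatectomy, 30% node-positive, sensitivities 45% and 65%, level 0.01, power 80%. These give 200 × 0.75 = 150 prostatectomies, with 150 × 0.30 = 45 node-positive and 105 node-negative patients expected. From 10.3.2 c): cut-offs of 65% and 90%, each in 2 of 3 readers. The plan does not give true specificity, reader correlation or reclassification counts, so values for these are assumed below.

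**Reproducing 61.** A one-sided 0.01 one-sample test of 65% against a fixed 45%, by normal approximation:

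n = [(2.326 × √(0.45 × 0.55) + 0.842 × √(0.65 × 0.35)) / 0.20]² = 60.74, rounded up to 61 (power at 61 is 80.2%).

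The two-sided version gives 70.8. A McNemar test with 61 pairs and a 20-point difference reaches 80% only if total discordance is about 0.22 (two-sided) or 0.25 (one-sided). The smallest possible discordance is 0.20, and the plan states none. So 61 is not an arithmetic error, but its origin is not identified.

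**Sensitivity half at true sensitivity 65%.** *Demonstrate* is read as the observed point estimate, which is an assumption because no bound or test is named. For one reader, q = P(X ≥ ⌈0.65n⌉) with X ~ Bin(n, 0.65). For at least 2 of 3 independent readers the probability is 3q² − 2q³. Before reclassification:

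| Node-positives | Needed | One reader | 2 of 3 readers |
|---|---|---|---|
| 44 | 29 | 0.519 | 0.528 |
| 45 | 30 | 0.475 | 0.463 |
| 46 | 30 | 0.555 | 0.582 |
| 61 | 40 | 0.521 | 0.532 |

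The jump from 46% at 45 to 58% at 46 is rounding of the required count (30/45 is 66.7%), so it is better to average over the count. Over Bin(150, 0.30) the result is 0.518. Over Bin(300, 0.30) and Bin(600, 0.30), which is two and four times the enrolment, it is 0.510 and 0.507. Reader correlation moves the sensitivity half by only about 1 point at 65%.

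**Whole rule.** For k node-positives among 150, multiply the sensitivity half at k by the specificity half at 150 − k, then average over k ~ Bin(150, 0.30). Independent readers, no reclassification:

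| True sensitivity | Specificity 0.90 (assumed) | Specificity 0.95 (assumed) |
|---|---|---|
| 60% | 0.088 | 0.163 |
| 65% | 0.278 | 0.518 |
| 70% | 0.465 | 0.867 |
| 75% | 0.529 | 0.986 |
| 80% | 0.535 | 0.999 |

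With latent reader correlation 0.8, the 70%/0.95 entry falls from 0.867 to about 0.80. The 65% entries barely move.

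**Reclassification.** Each patient added under i)(2) enters both numerator and denominator of sensitivity. Adding 1, 2, 3 or 5 such patients (assumed counts) raises the averaged sensitivity half from 0.518 to 0.582, 0.643, 0.700 or 0.799.

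Region mismatch under iii)(2) affects both halves. With mismatch in 5% of node-positives (assumed), removing them from the sensitivity denominator gives an expected sensitivity of 0.60/0.95 = 63.2% if the assumed 65% ignores region, or 0.65/0.95 = 68.4% if it already requires region agreement. The sensitivity half is then 0.371 or 0.776. The same patients become false positives. With two of them added to 105 node-negatives, 97 true negatives are needed (0.90 × 107 = 96.3) instead of 95. The 2-of-3 specificity half falls from 0.526 to 0.175 at true specificity 0.90, from 0.878 to 0.552 at 0.92, and from 0.999 to 0.982 at 0.95.

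**The case against.** Section 10.2.1 says openly which comparison drives the calculation, and the primary objective in the Synopsis and section 2.5 is estimation of accuracy. A careful reader is therefore not wholly misled. This limits the weight of the point but does not remove it: the same paragraph says the number powers the primary aim, and 10.3.2 c) gives that aim a pass/fail rule of another kind.

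It can also be said that the real chance of success may be higher than half. True sensitivity may exceed 65%, and i)(2) can add true positives. Both are correct. At 70% sensitivity and 0.95 specificity the rule is met about 87% of the time with independent readers. But the plan assumes 65% and gives no reclassification count, so neither argument makes 80% the power of this rule. Reading *demonstrate* as a lower confidence bound does not rescue it either: at a true 65%, success per reader would then be only about the one-sided error level.

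Two stronger readings are tempting. One is that the primary aim truly has about 50%, or 28%, power. The documents do not support a single figure, because specificity, reader correlation and reclassification are all unstated. The other is that 61 came from a one-sample test and cannot be a McNemar power. The one-sample match is close, but section 10.2.1 names no test, and McNemar also fits at a discordance the plan neither states nor excludes.

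**Conclusion.** The point stands in this form: the stated 80% is not a property of the primary success rule, the plan gives no power for that rule, and the rule's sensitivity cut-off coincides with the assumed truth.

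At the plan's own 65%, the sensitivity half is met about half the time. The specificity half can only lower the chance of overall success below that of the sensitivity half. These figures assume point-estimate cut-offs, independent readers and no reclassification; the specificities are illustrative. Reclassification under i)(2) can raise the sensitivity half. Region mismatch changes the sensitivity denominator and also adds false positives, so a high figure for the sensitivity half alone says little about the whole rule. The difference between the 45 node-positives expected and the 61 required is a separate matter and is not relied on here.

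**What to change.** In 10.2.1, stop describing the 80% as power for the primary aim. Label it as power for the exploratory comparison with conventional imaging, and name the test and sidedness used. If it was a McNemar calculation, state the assumed discordance; if it was a one-sample test against a fixed 45%, say so.

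Add one table giving the probability of meeting the 10.3.2 c) rule over true sensitivity 60–80% and true specificity 0.90–0.95, averaged over the random number of node-positives among the 150 expected prostatectomies. State with it that the cut-offs apply to point estimates (if that is intended), the assumed reader correlation, and the assumed numbers reclassified under i)(2) and iii)(2), carried through both sensitivity and specificity.

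The cost is wording and one table, with no new patients, no new data and no change to the success criterion. The drawback is that, at the assumed 65% and before reclassification, the stated chance of primary success becomes less favourable than 80%.
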